### Recruitment Estimates by Hospital

Participating Hospital	no. beds	Annual Admissions	Observed Eligible Patients* (annualized)	Estimated Annual Consults**	Annual recruitment assuming 50% refusal (range of observed - estimated)
Aiken Hospital, SC	243	3767	264	188	132-94
Russell Hospital, AL	80	1506	240	109	54
Highland Hospital, MS	33	1200	296	51	148-25

\*Hospitals estimated eligible patients based on study eligibility criteria  
\*\*CAPC estimates of consults based on 5-7% of annual admissions

### V. Study Duration and Timeline

**Enrollment:** September 2019 [Anticipated]

**Primary Completion:** January 2023 [Anticipated]

**Study Completion:** September 2023 [Anticipated]

### Study Timeline \*Subject to Change\*

ACTIVITY	2018				2019				2020				2021				2022				2023				
	Sept.	Oct.	Nov.	Dec.	Jan.	Apr.	Jul.	Oct.																	
IRB approval																									
Build relationships with hospital staff, orient to study & eligibility criteria																									
PC MD training in culturally-based tele-consult																									
Establish CAG, provide orientation & training																									
CAG quarterly meetings																									
Patient enrollment																									
Data collection																									
Data analysis																									
Progress reports/final reports																									
Presentations and publications																									

### VI. Inclusion and Exclusion Criteria

#### Patient Inclusion Criteria:

- (1) AA or W;
- (2) > 65 years old; has a condition which fits into one of 3 illness paradigms (including: cancer, cardiac disease, pulmonary disease, neuro-degenerative disease, renal disease, stroke, sepsis, hepatic disease)
- (3) Clinician answers “no” to question: “Would you be surprised if this person died in the next 12 months?”
- (4) Patient has a caregiver who has been involved in their care.
- (5) Able to complete baseline interviews.

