## **II. Aims of the Study**

The aims of this study are to compare a robust, culturally-based tele-consult program to usual hospital care to:

- a. Primary Aim:** Determine whether a culturally-based PC tele-consult program leads to lower symptom burden in hospitalized AA and W older adults with a life-limiting illness.
- b. Secondary Aim:** Determine whether a culturally-based PC tele-consult program results in higher patient and caregiver quality of life, care satisfaction, and lower caregiver burden at Day 7 post-consultation, and lower resource use (hospital readmission, emergency visits) 30-days post-discharge
- c. Exploratory Aim:** Explore mediators and moderators of patient symptom and caregiver burden outcomes.

[figure not shown]

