#### IV. Study Design

This study consists of 2 phases:

**Phase I Convening & Soliciting CAG Participation in study design.** This phase will consist of assembling CAG members to review study procedures and some CAG members will be trained to approach potential study participants. Potential CAG members (8, with equal numbers of AA and W) will be identified by the hospital staff and community leaders of each of the three sites, and invited to participate in the CAG. Potential CAG members will include respected members of the community, those who have recently lost a loved one and understand end of life care, and community leaders. Potential members will be discussed by the recruiters with the study PIs to ensure there is socio-demographic balance, and equal representation of African American and

White members, to ensure all will feel comfortable participating and contributing, and to ensure that they are not all from the same family/church/social group. Following this step, a formal written invitation will be extended to those selected, followed by a phone call by the Study Manager.

**Phase II Conducting the RCT.** In Phase II, we will conduct a randomized controlled trial (RCT) at the 3 sites to test the effectiveness of this innovative program. We will recruit 352 hospitalized AA and W adults over age 65 whose treating physician would not be surprised if they died within the next year and the patients' family/friend caregiver. Half of the patient participants (N=176) will be randomized to receive usual care appropriate to their illness. Patients randomized to usual care in each of the three participating hospitals will receive inpatient care appropriate to their illness. This includes assessment and treatment by the admitting physician, along with any subspecialists that are consulted. The formulation and sharing of prognostic information and the engagement of patients and families in establishing goals of care will be according to the standards of the admitting physician and subspecialists. Treating clinicians may include hospitalists, nurse practitioners, social workers, pastoral care, and occasionally, the patient's primary care practitioners who have hospital privileges.

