### **Consent Process:**

**a. Approaching the patient and family:** The CSC will screen admissions each weekday and will only approach potential study participants after confirming eligibility (e.g. “surprise question”) and getting approval from the treating clinician.

**b. CAG and CSC meet with patient and family:** Following approval, the CSC will contact the CAG member “on-call” for the day to speak with the patient. The CAG member and CSC will approach the patient. The CAG member will introduce themselves and the CSC, and describe the study to the patient. The CAG will emphasize their role in developing the study and how this study was designed to help the community. If the patient indicates that he/she would like to participate, the CSC will provide an overview of the study, including a description of palliative care, the tele-consult equipment and process, (if randomized to that group), and randomization using a simple visual diagram. (These materials were developed by the R21 CAG and will be reviewed and adapted by each hospital-specific CAG). The CSC will then read the consent form to all patients (assuming no or limited literacy) unless the patient prefers to read it themselves. The family member is invited to participate and will sign a separate consent agreeing to complete questionnaires regardless of group assignment. The CSC will assist the patient (and separately the family member) to complete the baseline questionnaires using an electronic tablet that connects directly to the REDCap database. Baseline data are collected prior to randomization, so study coordinator blinding is not necessary.

The CSC will screen, obtain consent and organize the tele-consult. The CSCs will remain in daily contact with hospital staff and participate in team meetings to remind clinicians about eligibility criteria. Team meeting attendance will allow the CSC to clarify the study goals and protocol and to strategize solutions if challenges arise. The BSC will collect all data following patient randomization.

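### Baseline ESAS is collected before randomisation, but the stated analysis does not use it as a covariate in the Day 7 comparison or name it as a moderator

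*Combined protocol and SAP*

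**What the plan says.** - **Aim.** Section II asks whether the programme "leads to lower symptom burden in hospitalized AA and W older adults with a life-limiting illness". The exploratory aim is to "Explore mediators and moderators of patient symptom and caregiver burden outcomes".
- **Entry.** Section VI requires African American or White race, age over 65, that the patient "has a condition which fits into one of 3 illness paradigms", a surprise-question answer of no, an involved caregiver, and ability to complete the baseline interviews. The exclusions are inability to be interviewed, current hospice care and no caregiver. Section IV describes the same population as "adults over age 65 whose treating physician would not be surprised if they died within the next year". None of these refers to symptoms.
- **Measurement.** Table 5 (section X) marks the nine-item ESAS at baseline and Day 7. Section IX states: "Baseline data are collected prior to randomization".
- **Analysis.** Section VII stratifies by site, race and illness trajectory. Section XI puts into the regression models those demographics and stratification variables found to differ between arms, with race entered separately. Baseline ESAS is not mentioned. The section announces regression models, but none appears in the text supplied.
- **Moderators.** Under the exploratory aim, Table 5 as supplied has a row for mediators and none for moderators.
- **Size.** Section IV: "We will recruit 352 hospitalized AA and W adults over age 65", 176 per arm. The text supplied gives no effect size, SD, alpha, power or dropout for this number.

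**The concern.** The surprise question measures prognosis. A patient expected to die within a year may still have a low ESAS score on the day of enrolment, and a score near the bottom of the scale has little room to fall. If such patients are a noticeable share, the average Day 7 difference may be smaller than the difference among patients with symptoms to relieve.

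A null average could then mean either of two things: the programme does not relieve symptoms, or it relieves them in those who have them and the average hides it. Baseline ESAS is the measurement that helps to separate these readings. It is also a natural covariate for the Day 7 score, because it is the same instrument in the same patient about a week earlier. The stated plan uses it for neither purpose.

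**Working it through.** **1. The plan's own figure.** 352 cannot be reproduced, because its inputs are not in the text. With 176 per arm, SD 1, two-sided 5% and no dropout (all assumed), the standard error of the difference is sqrt(2/176) = 0.1066 SD. The detectable difference is (1.960 + 0.842) × 0.1066 = 0.30 SD at 80% power and (1.960 + 1.282) × 0.1066 = 0.35 SD at 90%. Other inputs also reach 352 (0.40 SD, 90% power, 25% dropout), so no assumption can be attributed to the sponsor.

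**2. Illustration of dilution.** Let a share f have no treatment effect and the rest an effect d. The average effect is d(1 − f), and power = Φ(d(1 − f)/(0.1066 × s) − 1.960). With a common SD, s = 1. If low-symptom patients have SD 0.5, s = sqrt((1 − f) + 0.25f). That second case leaves out the variance caused by the two groups having different means, which adjustment for baseline would largely remove. Both f and d are assumed.

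| f | d = 0.40, common SD | d = 0.40, SD 0.5 in low group | d = 0.30, common SD | d = 0.30, SD 0.5 in low group |
|---|---|---|---|---|
| 0% | 96% | 96% | 80% | 80% |
| 20% | 85% | 90% | 61% | 68% |
| 30% | 75% | 85% | 50% | 61% |
| 50% | 47% | 66% | 29% | 43% |

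The d = 0.30 columns use the unrounded 0.2986. Worked cell for d = 0.40, f = 20%, common SD: 0.32/0.1066 = 3.002; 3.002 − 1.960 = 1.042; Φ = 85%. With SD 0.5 in the low group: s = sqrt(0.85) = 0.922; 3.002/0.922 − 1.960 = 1.296; Φ = 90%.

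The table shows direction and sensitivity. It does not estimate this trial's power.

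**3. What adjustment gains.** With correlation r between baseline and Day 7 ESAS within arm, adjustment multiplies the variance of the treatment estimate by about (1 − r²). The documents do not give r. Any non-zero value helps, and the cost is one degree of freedom. Under the stated rule this gain is not taken, because baseline ESAS is neither a demographic nor a stratification variable.

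**4. How precise the moderator analysis can be.** Take baseline ESAS centred, in units of its own SD, and residual SD 1. The interaction coefficient has standard error sqrt(4/352) = 0.1066 per baseline SD. Then, with 95% half-widths:

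- overall effect: 1.96 × 0.1066 = 0.21 SD
- effect at one SD below or above the mean baseline: 1.96 × sqrt(2) × 0.1066 = 0.30 SD
- difference between those two effects: 1.96 × 2 × 0.1066 = 0.42 SD

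A difference of 2.80 × 2 × 0.1066 = 0.60 SD would be needed for 80% power. Dropout widens all of these. The analysis describes the pattern and is unlikely to settle it.

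**The case against.** A reader might infer that eligibility is wrong and should carry a symptom threshold. The documents do not support that. Section I frames the programme around access to, and acceptability of, palliative care for seriously ill rural patients. The secondary aims cover quality of life, satisfaction, caregiver burden and resource use, and a symptom threshold would narrow all of these for the sake of one outcome. The Day 7 comparison is unbiased for the population enrolled.

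A reader might also take the power table as a demonstrated loss. Three things count against that.

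- The overview describes seriously ill hospitalised patients as suffering uncontrolled symptoms, so the low-symptom share may be small. No ESAS figure is given either way.
- The aim compares arms at Day 7. A patient with few symptoms at entry can worsen within the week, and the programme may limit that, so a zero effect in this group is an extreme assumption.
- Patients near the floor probably vary less, and the common-SD columns ignore this.

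Finally, a reader might infer from the recruitment table ("Annual recruitment assuming 50% refusal") that the sites have patients to spare for a stricter entry rule. The low-end figures rest on consults as a percentage of all admissions. Turning annual rates into a surplus over 352 also assumes full-rate accrual at every site from the first month to the last. That is too weak a basis for changing eligibility.

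All of this stands against changing who is enrolled. None of it is a reason to leave baseline ESAS out of the analysis. One reservation remains: section XI points to models that are not in the text supplied. If they already contain baseline ESAS and the interaction, the sponsor need only show where.

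**Conclusion.** The point holds as a gap in the analysis plan, not as a fault in eligibility and not as a bias. The stated covariate rule leaves out baseline ESAS, and the exploratory aim promises moderators without naming one. The consequences are lost precision, of unknown size because r is not given, and a null average result that is harder to interpret.

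Any loss of power from low-symptom patients is conditional on an assumed share and an assumed effect. At a 20% share and 0.40 SD it is 96% to 85% with a common SD, and 96% to 90% if the low group has half the SD. The remedy recovers precision and helps interpretation. It does not remove dilution of the average effect.

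**What to change.** Leave the eligibility criteria as they are. In section XI, with a matching row in Table 5:

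1. State that the primary Day 7 ESAS model includes baseline ESAS as a continuous covariate, whether or not the arms differ at baseline. Use the same ESAS score as the primary outcome.
2. Name arm by baseline ESAS (continuous) as the first exploratory moderator analysis, fitted in a separate model so that the primary estimate is unaffected.
3. Report the treatment effect with 95% confidence intervals at a low and a high baseline value fixed in advance (for example, one SD below and above the mean), beside the overall result and labelled exploratory.
4. Report the baseline ESAS distribution by arm, so that readers can see how many patients had few symptoms.

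The cost is some SAP text, one covariate, one separate model and an extra table row. No new data are needed. The downside is an interaction estimate that will be imprecise at 352: an interval that includes zero should not be read as showing that the effect is the same at all symptom levels.

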#### Patient Exclusion Criteria:

- (1) Unable to complete baseline interviews;
- (2) Currently receiving hospice care;
- (3) No family member/caregiver.

Caregiver Inclusion Criteria:

- (1) Age  $\geq 21$  years
- (2) English-speaking
- (3) Community-dwelling
- (4) Not a “sitter”

## **VII. Randomization Plan**

The randomization scheme will be executed via REDCap, a clinical trials management software program. Participants will be randomly assigned to group (1:1) using a computer-generated program overseen by [name]. The randomization scheme will be stratified by site (SC, AL, MS) race (W, AA), and illness trajectory. As the Central Coordinating Site, UAB will manage the randomization process. The UAB study manager will be alerted to the assignment by REDCap and will trigger the local unblinded study coordinator to communicate assignment to the participant and initiate study protocol. All other members of the research team will remain blind to group assignment and participants will be instructed not to discuss their assignment with the local study coordinator collecting the outcome assessments.

## **VIII. Community Advisory Groups (CAGs)**

The community advisory groups (CAGs) will be an integral part of the study. A CAG will be formed at each of the three study sites. Each CAG will be made up of eight members, with equal numbers of African American (AA) community members (four), and White (W) community members (four). Potential CAG members will be identified by hospital staff and community leaders and will include respected members of the community, or those who have recently lost a loved one and understand end of life care.

**The role of the a CAG** members on the study is three-fold:

**a. Advisory:** CAG members will be invited to meet with the study team members and PC physicians every three months throughout the study, hear about progress, and challenges, and provide advice when problems arise. The last meeting of this study will be a full report-back and summary to the CAG.

**b. Cultural recognition:** CAG members will meet with and be trained by the CAG members from Beaufort, South Carolina, who developed the pilot study. We anticipate that the appreciation for and recognition of the southern rural African American or White culture by this study, and a recognition that the community has been instrumental in creating a program that could benefit their community, will result in an appreciation for the potential value of this study.

**c. Introducing patients to the study:** The CAG member will be the first to meet potential study participants (regardless of which group they get randomized to) to introduce them to the study, and will introduce the CSC. CAG members will be the first to meet potential study participants (regardless of which group they get randomized to) to introduce them to the study. The role of the CAG member in meeting with patients is primarily to make the patient and caregiver feel at ease, and to help build trust. In the pilot study, we found that if an African American CAG member met with an African American patient and caregiver, it helped to address feelings of mistrust in the research study. Particularly helpful was that the pilot CAG members assured patients and caregivers of their belief in the study, and their confidence and trust in the palliative care (PC) physician. CAG members will receive gas cards to cover their travel expenses to and from the hospital.

Before study recruitment begins at the hospital site, the coordinating study coordinator will create a CAG member schedule and telephone tree, to determine which CAG members will be ‘on call’ each day, and the best way to reach them. This will facilitate the quick action needed to meet with potential study participants after they have been identified and permission has been granted.

## **IX. Patient Recruitment and Consent Process**

Each site will have two part-time study coordinators: a) Coordinating Study Coordinator (CSC) and b) Blinded Study Coordinator (BSC).

### **Consent Process:**

**a. Approaching the patient and family:** The CSC will screen admissions each weekday and will only approach potential study participants after confirming eligibility (e.g. “surprise question”) and getting approval from the treating clinician.

**b. CAG and CSC meet with patient and family:** Following approval, the CSC will contact the CAG member “on-call” for the day to speak with the patient. The CAG member and CSC will approach the patient. The CAG member will introduce themselves and the CSC, and describe the study to the patient. The CAG will emphasize their role in developing the study and how this study was designed to help the community. If the patient indicates that he/she would like to participate, the CSC will provide an overview of the study, including a description of palliative care, the tele-consult equipment and process, (if randomized to that group), and randomization using a simple visual diagram. (These materials were developed by the R21 CAG and will be reviewed and adapted by each hospital-specific CAG). The CSC will then read the consent form to all patients (assuming no or limited literacy) unless the patient prefers to read it themselves. The family member is invited to participate and will sign a separate consent agreeing to complete questionnaires regardless of group assignment. The CSC will assist the patient (and separately the family member) to complete the baseline questionnaires using an electronic tablet that connects directly to the REDCap database. Baseline data are collected prior to randomization, so study coordinator blinding is not necessary.

The CSC will screen, obtain consent and organize the tele-consult. The CSCs will remain in daily contact with hospital staff and participate in team meetings to remind clinicians about eligibility criteria. Team meeting attendance will allow the CSC to clarify the study goals and protocol and to strategize solutions if challenges arise. The BSC will collect all data following patient randomization.

## **X. Description of Tele-consult Intervention**

**Tele-consult Intervention.** The tele-consult intervention consists of 3 interactions between the remote palliative care physician/interdisciplinary team (IDT) and the local patient/caregiver and hospitalist/treatment team.

Community-developed, Culturally-Based Inpatient Teleconsult- Intervention				
Contact #	When	With Whom	Method	Purpose
#1 Palliative Care Tele-consult	As soon after randomization as possible	Patient (family) referring hospitalist & remote palliative clinician  Local Study coordinator  Remote IDT Members	Secure tele-consult  Remote IDT review  eHR document	1. Conduct community-developed, culturally based palliative assessment. 2. IDT review 3. Develop recommendations & palliative care plan
#2 Follow up Day 3	Within 3 days post consult	Remote & local clinicians	eHR document  Telephone	1. Provide recommendations & care plan 2. Respond to patient, family & remote team questions 3. Identify community care team & initiate referrals as needed (including primary clinician/hospice provider if appropriate).
#3 Follow up Day 6	Within 6 days post consult	Remote Clinician  Patient/family & local community care team members	Telephone	1. Reassess patient and care plan 2. Assess adequacy of discharge plan or home experience 3. Refer to community resources

**Contact #1:** the Coordinated Study Coordinator [CSC] will work closely with the patient/family, local team, and remote palliative care physician to determine a time suitable (within 48 hours on weekdays) to perform the Tele-consult. The CSC and the hospitalist/a member of the treatment team will be in the room with the patient and family. The CSC will set up the HIPAA protected telehealth laptop next to the patient's bed, introduce the patient to the remote palliative physician, and the tele-consult will proceed. All Tele-Consults are digitally-recorded within the secure portal. Most consults take 45-60 minutes. To ensure a comfortable conversation with

minimal interruptions we have instituted several steps including checking with floor nurse, putting up signs on the door, and tasking the CSC with running interference in case of interruptions.

Within 24 hours of conducting the Tele-consult, the remote palliative physician will seek an interdisciplinary team review, develop the plan, and make recommendations, which may include immediate patient care (e.g., symptom relief) and continuing care, related to the hospital stay and following discharge. Recommendations may also include referrals to other supportive resources such as a hospital social worker or pastor. The written consult will be documented using a standardized note template that corresponds to the 8 NCP palliative care domains and will be provided via a secure HIPAA-compliant portal that will be part of the patients' inpatient medical record. As needed, verbal contact will also occur between the palliative care physician and the hospitalist staff.

**Contact #2** Day 3 (approximately 24-48 hours after first contact). The CSC will arrange a follow up videoconference between the remote palliative care physician and patient if in hospital or via phone if the patient has been discharged. The purpose of this second contact is to determine how patient is progressing, if the plan was implemented, if hospital staff/patient has encountered any challenges or questions, and to determine who will be assuming the patient's care in the community. Documentation of the contact will be provided as described above.

**Contact #3** Day 6 (post consult) (via videoconference if patient is in hospital, via phone if discharged.) To determine if patient is experiencing new or ongoing challenges, to confirm availability of community or hospice care as appropriate.

**Tele-consult Intervention + Usual Care.** In the usual care group and the intervention group, a study coordinator at each site will administer questionnaires to the patient and their designated family/friend caregiver, in person or telephone (if patients are discharged during the study period) at baseline (T1), Day 7 (T2) and Day 30 after hospital discharge (T3). (Study coordinators administering T2/T3 assessments will be blinded to study group- aka Blinded Study Coordinators [BSC]).

Table 5. Measures and Data Collection Schedule						
Construct	Instrument & Description	# of Items	T1 Baseline	T2 Day 7	T3 Day 30	
Demographics	Demographic Questionnaire- Age, gender, race/ethnicity, marital status, religion, education, occupation, insurance status, financial status.	10	X			
Primary Aim						
Symptom Burden	Edmonton Symptom Assessment Scale (ESAS) - symptom intensity using visual analog	9	X	X		
Secondary Aims						
Patient and Caregiver QoL	PROMIS Global Health -10. Evaluates physical, social, and emotional health in healthy & chronically ill adults	10	X	X		
Family Satisfaction with Care	FamCare - family satisfaction with availability of care, physical & psychosocial care, information giving	20	X	X		
Patient Satisfaction with Care	Feeling Heard and Understood - Self-report quality measures for palliative care settings on Likert scale (1 item)	1	X	X		
Caregiver Burden	Montgomery Borgatta Caregiver Burden Scale (MBCB)-subscales objective, subjective, demand burden	14	X	X		
Resource Use	Hospital admission, ED visit, hospice	NA			X	
Exploratory Aim						
Mediators	Consult recommendations implemented by Hospitalist & Pt	NA		X		

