The other half of the patient participants (N=176) will receive the culturally-based palliative care consult. Patients in the intervention group will receive usual care as described above, and, in addition, will participate in a standardized, comprehensive palliative care Tele-consult

assessment as well as a follow up by the palliative care physician on Day 3 and 6 following the initial consult.

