## **XI. Statistical Analysis Plan**

Demographic variables (e.g., age, sex, race, disease) will be summarized and compared across treatment groups using t-tests and nonparametric Wilcoxon signed rank tests for continuous measures (age), binomial tests (sex, race), and chi-square statistics for categorical variables (e.g., marital status, education). All demographics and stratification variables found to differ across treatment groups will be included in regression models (referred to as the vector  $ZZ_{ii}$  in the regression models to follow); however, race will be included in the final models separately from the vector  $ZZ_{ii}$  vector. Tabulations of binary and categorical variables will be presented for all measures and broken down by treatment group. Age will be summarized by mean and standard deviation for all participants, and broken down by treatment group.

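### The plan collects no baseline measure of prior hospital or ED use, so the 30-day readmission and ED-visit comparisons give up a small amount of precision that two short pre-randomisation items and one SAP sentence could recover

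*Combined protocol and SAP*

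**What the plan says.** Section II lists among the secondary aims "lower resource use (hospital readmission, emergency visits) 30-days post-discharge". Table 5 in Section X gives the matching row, "Hospital admission, ED visit, hospice", a single mark under T3 (Day 30 after discharge).

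The other five outcome rows are marked at both T1 and T2: the ESAS, PROMIS Global Health-10, FamCare, the Heard and Understood item, and the caregiver burden scale. The Mediators row also lacks T1, but it records whether consult recommendations were implemented, which is a process that follows the consult and not an outcome.

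No other form fills the gap. The T1 demographic questionnaire covers age, gender, race/ethnicity and "marital status, religion, education, occupation, insurance status, financial status". The data collection sheet in Section XII lists readmissions but nothing before the index stay.

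On covariates, Section XI says "All demographics and stratification variables found to differ across treatment groups will be included in regression models", with race entered separately. It mentions regression models that are to follow, but none appears in the text. Section VII stratifies randomisation by site, race and illness trajectory.

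**The concern.** A patient's recent admissions and ED visits are a natural predictor of further admissions and ED visits. A covariate measured before randomisation that predicts the outcome removes variance from the treatment comparison without affecting its validity. The plan collects such a covariate, in the form of a baseline score, for every outcome except this one. The eligible population covers eight disease groups, so prior use may well vary widely between patients.

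At stake is the precision of two secondary comparisons. The primary endpoint is not affected.

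**Working it through.** **Plan's own figure.** Section IV: "We will recruit 352 hospitalized AA and W adults over age 65", with 176 in each arm. 2 × 176 = 352, which agrees with 1:1 allocation. The basis for 352 cannot be reproduced, because no alpha, power, effect size or dropout is stated.

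**Assumptions (none is in the documents).** Two-sided alpha 0.05; prior use (yes/no) in 30-50% of patients; odds ratio 1.5-4 for the outcome given prior use; outcome rate 15-30%; no loss, or 30% loss, by Day 30.

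**Step 1: variance explained.** For a yes/no item with prevalence q and outcome risks p_a (prior use) and p_b (none), averaging to p:

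R² = q(1 − q)(p_a − p_b)² / [p(1 − p)]

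Example: q = 0.5, p = 0.30, odds ratio 3 gives p_a = 0.411, p_b = 0.189 and R² = 0.25 × 0.222² / 0.21 ≈ 0.059.

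| Odds ratio | R² over the assumed q and p |
|---|---|
| 1.5 | 0.5-0.9% |
| 2 | 1.5-2.5% |
| 3 | 3.4-5.9% |
| 4 | 5.1-9.3% |

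A count gives much the same range. With an overdispersed prior-admission count (mean 1, capped at 6), a 22% readmission rate and log odds ratios of 0.20, 0.35 and 0.50 per admission, r is about 0.12, 0.22 and 0.32, so r² is about 1.5-10%. I carry forward R² of about 1-10%.

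**Step 2: precision.** SE ratio = √(1 − R²); equivalent extra patients = 352/(1 − R²) − 352.

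| R² | SE ratio | Extra patients |
|---|---|---|
| 0.01 | 0.995 | 3.6 |
| 0.02 | 0.990 | 7.2 |
| 0.05 | 0.975 | 18.5 |
| 0.10 | 0.949 | 39.1 |

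**Step 3: power.** Two-proportion test with n per arm replaced by n/(1 − R²), and p̄ the mean of the two rates:

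power = Φ{[|p₁ − p₂| − 1.96√(2p̄(1 − p̄)/n)] / √([p₁(1 − p₁) + p₂(1 − p₂)]/n)}

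| Comparison | R² = 0 | 0.01 | 0.02 | 0.05 | 0.10 |
|---|---|---|---|---|---|
| 30% vs 20%, 176 per arm | 58.2% | 58.7% | 59.1% | 60.4% | 62.8% |
| 20% vs 10%, 176 per arm | 75.0% | 75.4% | 75.8% | 77.1% | 79.3% |
| 30% vs 20%, 30% loss | 44.1% | 44.5% | 44.8% | 46.0% | 48.0% |

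Across these rows the gain is about 0.4 to 4.6 points.

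**Step 4: simulation check.** Risk difference adjusted by a linear model, n = 352, 30% vs 20%, half with prior use, 4,000 runs per setting. The ratio of adjusted to unadjusted SE was 0.988, 0.972 and 0.960 for odds ratios 2, 3 and 4. The mean estimate was about 0.10 in size with and without adjustment, so leaving the covariate out does not bias the comparison.

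**The case against.** The strongest reply is that the row is scheduled differently because it is a different kind of outcome. Readmission and ED visits after discharge are new events. Every patient is in hospital at T1 and current hospice users are excluded, so no same-state baseline exists of the kind the ESAS has. This stands: the proposal is a new prognostic covariate with a chosen look-back window, not the repair of an error, and it does nothing for hospice use.

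Stratification is a second fair point. Any part of prior use that follows illness trajectory or site is already balanced by design, so the added gain would be smaller than shown. Third, larger gaps sit nearby: no model is stated for resource use, and there is no rule for deaths before Day 30.

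Four stronger readings are tempting but not supported.

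- **Only resource use goes unadjusted for its own baseline.** Section XI states no baseline-outcome adjustment for any endpoint, the ESAS included. What differs is whether the data are collected.
- **Adjustment would be impossible later.** Prior events predate randomisation and might be found in hospital records. The documents plan no such search, which is a weaker statement.
- **Chance imbalance is a further harm.** The SE of a standardised arm difference is √(2/176) = 0.107, so an imbalance above 0.2 SD has about a 6% probability. At an assumed r of 0.3 it would move the result by 0.3 × 0.2 = 0.06 SD, or 0.56 of an SE. The confidence interval and type I error already allow for this; it is the same precision loss seen from another side.
- **The gain is 15-67 patients.** That follows from r = 0.2-0.4 (352/(1 − r²) = 367 to 419), but no document gives such a correlation, and the binary-outcome calculations above support about 39 at most.

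**Conclusion.** The point holds as a minor, optional improvement. The schedule fact is certain: Resource Use is the only outcome row without a T1 entry, and no listed form supplies prior use. The consequence is a small loss of precision and no bias. Its size rests wholly on assumed values: with 1-10% of variance explained, the SE would fall by about 0.5-5%, worth about 4-39 patients on 352 or roughly 0.5-5 power points. Stratification would make the true figure smaller to an unknown degree.

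**What to change.** 1. **Table 5, T1.** Add two counts for the 6 months before the index admission: hospital admissions, excluding the index stay, and ED visits. Take them before randomisation, either from the patient or caregiver on the baseline tablet or from the hospital record.
2. **Section XI.** Pre-specify log(1 + count) as a fixed covariate in the readmission and ED-visit comparisons whether or not the arms differ on it. The new items alone would change nothing, because the present rule brings in only demographics and stratification variables found to differ.
3. **Reporting.** Give a standardised (covariate-adjusted) risk difference. In a logistic model the gain does not show as a smaller SE of the conditional log odds ratio.

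The cost is two short questions or a record look-up, one sentence on the model and one on reporting. The downsides are slight extra burden on seriously ill patients and some recall error, which cannot depend on the assigned arm because collection precedes randomisation. Hospice use is not covered by this change.
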